In previous studies with Phased RFA an average acute procedural success of 98.2% (93-100%) was reported in patients with paroxysmal AF (23 studies). This is similar to the average acute procedural success reported for patients (6 studies) with persistent AF of 96.3%. In the case of index procedural failure, the authors linked the failure to the patient anatomy or characteristics and not to the Phased RFA system.

Endpoint definition:

- Procedure attempt was not declined due to technical issues related to Phased RFA system
- Only PVAC catheter(s) used to achieve PVI
AND
- All accessible PVs were isolated (entrance and/or exit block confirmation per vein)

If exit or entrance block was not verified during the procedure the data will not be used for this analysis.

Analysis Method: Acute procedural success rate will be reported as frequency and percentage at both the patients and vein level. Acute procedural success rate by patients will be calculated as number of patients with acute procedural success divided by number of patients with an attempted Phased RFA procedure. Acute procedural success rate by vein will be calculated as number of veins with electrical isolation verified divided by number of veins attempted with Phased RFA. 95% confidence intervals will be calculated using Fisher's exact method.

Limitation: Even though PVAC GOLD catheter has been designed anatomically, steerability can be influenced by the sheath used with the catheter. With fixed curve sheath might become challenging to reach all PVs, in particular right inferior PV due to technical issues. Due to this additional use of 3D system and irrigated catheters might be utilized by the medical centers where steerable sheath is not available.

Assess Phased RFA efficiency

Rational: The multi electrode catheter technology delivers continuous lesions and shortens procedure times. The ability to map and ablate with the same electrode simplifies and shortens the procedure.

Procedure duration is impacted by the maneuverability of the catheter. The new catheter design of the PVAC GOLD array allows enhanced tissue contact due to the 20° forward tilt.

Hospital resource allocation is another indicator of procedural efficiency, reflected by the procedure duration ("from skin to skin"), laboratory occupancy ("from door to door"), fluoroscopy time as well as number of used catheters and adjunctive devices (mapping and navigation) used.

Endpoint definition:

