**Table 3: Ranges**

Value	Range
Height	90 - 250 cm
Weight	30 - 500 kg
BMI (automatically calculated)	15 - 40
Age	18 - 120 years
Catheter PV cryo ablation - Total no.	1 - 4
Catheter PV rf ablation - Total no.	1 - 4
Catheter PV 3D RF ablation - Total no.	1 - 4
Number of pharmalogical cardioversions	1 - 99 Total no.
Number of electrical cardioversions	1 - 99 Total no.
Number of admissions	1 - 9 Total no.
Number of drinks/day	5 - 99
AF burden (optional)	0 - 100 %
Documented LVEF	15 - 70 %
Documented anteroposterior left aterial diameter	0 - 100 mm
INR value	0,5 - 9

General time of the procedure	30 - 300 min
LSPV	0 - 40 no.
LIPV	0 - 40 no.
LCPV	0 - 40 no.
RSPV	0 - 40 no.
RIPV	0 - 40 no.
RMPV	0 - 40 no.
Other accesery vein	0 - 40 no.
Number of pharmalogical cardioversions	1 - 20 Total no.
Number of electrical cardioversions	1 - 20 Total no.
Documented LVEF	0 - 100 %
Number of pharmalogical cardioversions	1 - 99 Total no.
Number of electrical cardioversions	1 - 99 Total no.
AF burden	0 - 100 %

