### 8.3.1 Characterize the acute procedural success rate

Success rates will be calculated for all documented procedures combined (patient level). Also, procedure success rates will be provided for first documented procedures, additional procedures, regular cases and training cases, separately. Success rates will also be shown per vein.

Success will be calculated for procedures that have been attempted (number of RF applications per patient > 0). Success rates will be provided for PVAC GOLD solely procedures (ancillary objective) and additionally for not PVAC GOLD solely procedures (using other catheter and/or using adjunctive devices).

If RF applications per patient, consumables (Phased RFA catheters used), successfulness and PV confirmation (exit or entrance block) was not verified for the procedure, the data will not be used for analysis. Consumables and procedure success will be taken from the procedure form. Relatedness of Phased RFA will be taken from AE form.

The procedure is considered successful if:

- Procedure attempt was not declined due to technical issues related to Phased RFA system and
- Only PVAC catheter(s) used to achieve PVI and
- All accessible PVs were isolated (entrance and/or exit block confirmation per vein)

This combined endpoint (variables linked via “and operation”) is applicable, if all conditions are available and complied.

Because of different procedure forms (eCRF V1.3 and eCRF V1.4), PVI achievement by PVAC GOLD only is assumed for patients documented by eCRF V1.3 as follows:

- [F21000010] Phased RFA catheter used: only PVAC GOLD is ticked, and
- [F22000010] to [F22000060] PVI confirmation: exit block and/or entrance block are ticked, and
- [F20001000] Number of RF applications per patient > 0

Unsuccessfulness per vein is considered, if the vein is not isolated or not verified. Percentages for success will be shown per vein for patients treated with PVAC GOLD solely. Precondition is that the number of RF applications per patient is greater than zero.

PVI achievement by PVAC GOLD only is defined for patients documented by eCRF V1.4 as follows:

- [F21000010] Phased RFA catheter used: only PVAC GOLD is ticked, and
- [F22000062] Where all PVs isolated at the end of the procedure = yes, and
- [F22000066] Where all PVs isolated by using PVAC only = yes, and
- [F21000010] Number of RF applications per patient > 0

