Unsuccessfulness per vein is considered, if the vein is not isolated or not verified. Percentages for success will be shown per vein for patients treated with PVAC GOLD, all PVs were isolated at the end of the procedure = no and all PVs isolated by using PVAC only = no.

**Table 9:** Procedure success variables from Procedure and AE form

Objective section	Definition (used variables)	Related FID's annotated eCRF (V1.3, V1.4)
Procedure attempt was not declined due to technical issues related to Phased RFA system	Procedure form: Date of procedure Phased RFA procedure successful?  No – Due to AE AE form: Date of AE Was the event related to technical issues?* Related/Possibly related	F20000010 F22000180 F22000190  F30000010 F30000070
Only PVAC catheter(s) used to achieve PVI	Procedure form: Phased RFA catheters used PVAC GOLD (solely) Number of RF applications per patient > 0  Were all PVs isolated at the end of the procedure Were all PVs isolated by using only PVAC	eCRF V1.3/V1.4 F21000010  F20001000 eCRF V1.4 only F22000062  F22000066

All accessible PVs were isolated (entrance and/or exit block confirmation per vein)	Were all accessible PVs isolated at the end of the procedure entrance block and/or exit block Exit block and/or Entrance block	eCRFV1.3/V1.4 F22000010 F22000020 F22000030 F22000040 F22000050 F22000060
---	--	---

\* Precondition: If the documented AE is related to technical issues with Phased RFA system components, the date of the latest procedure must be  $\leq$  date of the AE. For patients with more  $> 1$  procedure, the latest procedure will be the related procedure.

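### SAP 8.3.1 does not apply the accessible-vein criterion for acute success consistently across eCRF V1.3 and V1.4, so a patient with an unreachable vein can be scored differently by form version

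*SAP*

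**What the plan says.** Protocol 4.4.3 and SAP 8.3.1 give the same three conditions for acute success: the attempt was not declined for technical reasons, only PVAC catheters were used to achieve isolation, and "All accessible PVs were isolated (entrance and/or exit block confirmation per vein"). The SAP joins them by AND.

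The SAP then gives rules by form version for the second condition. For the older form, "PVI achievement by PVAC GOLD only is assumed for patients documented by eCRF V1.3 as follows": only PVAC GOLD ticked as catheter, RF applications above zero, and "F22000010] to [F22000060] PVI confirmation: exit block and/or entrance block are ticked". For the newer form it requires only PVAC GOLD ticked, RF applications above zero, "F22000062] Where all PVs isolated at the end of the procedure = yes", and "F22000066] Where all PVs isolated by using PVAC only = yes".

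Table 9 in the same section maps each condition to fields. It places F22000062 and F22000066 under the PVAC-only condition, marked as V1.4 only. It maps the third condition to F22000010 through F22000060 for both versions, with the wording "Were all accessible PVs isolated at the end of the procedure entrance block and/or exit block".

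Unreachable veins are foreseen. Protocol 4.4.3 notes under its limitations: "With fixed curve sheath might become challenging to reach all PVs, in particular right inferior PV".

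**The concern.** The criterion is about accessible veins, but the V1.4 items, as the SAP prints them, are about all veins. Because the conditions are joined by AND, the stricter V1.4 item overrides the accessible-vein condition for exactly the patients for whom the word accessible was included. V1.3 has no such item.

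Both forms are likely to contribute patients. SAP 1.1 dates V1.3 to April 2015 and V1.4 to January 2017, and the protocol synopsis plans recruitment from Q1 2015 to Q2 2018. The SAP pools them and plans no analysis of acute success by form version. A difference between earlier and later patients could then reflect the form rather than the procedure, and the pooled rate would mix two definitions.

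**Working it through.** The plan states no expected value or target for acute success, so there is no figure to reproduce. The check scores hypothetical patients under each rule and then illustrates the size.

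**Step 1: score patients.** Assumption: the six fields F22000010 to F22000060 are the left superior, left inferior, left common, right superior, right inferior and right middle veins. The annotated eCRF would confirm this. The SAP does not say what ticked covers on V1.3, so two sensible readings are shown. All patients except E were treated with PVAC only.

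| Patient | Third condition | V1.3, accessible veins ticked | V1.3, present veins ticked | V1.4 as printed |
|---|---|---|---|---|
| A: four veins, all isolated | met | pass | pass | pass |
| B: right inferior vein unreachable, other three isolated | met | pass | fail | fail |
| C: common left vein, all veins isolated | met | pass | pass | pass |
| D: right inferior vein accessible, not isolated | not met | fail | fail | fail |
| E: four veins isolated, one with a non-PVAC catheter not recorded in F21000010 (assumption) | met | pass | pass | fail, through F22000066 |

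Patient B is the point. On V1.4 as printed, B fails although the third condition is met. On V1.3, B passes if ticked refers to accessible veins. If it refers to present veins, the two forms agree on B, but both are then stricter than the stated criterion. Patient E shows a second difference: F22000066 has no V1.3 counterpart, so V1.3 may miss what V1.4 records.

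**Step 2: size.** Let s be the success rate under the accessible-vein criterion and u the share of patients with an unreachable vein. If s is the same with and without an unreachable vein, the V1.4 rate as printed is s × (1 − u). Inputs: s = 98.2% (paroxysmal AF) and 96.3% (persistent AF), the earlier-study averages in protocol 4.4.3, used only as illustration. No value of u is given in the documents; 0% to 10% is assumed.

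| u (assumed) | s = 98.2% | s = 96.3% |
|---|---|---|
| 0% | 98.2% | 96.3% |
| 2% | 0.982 × 0.98 = 96.2% | 0.963 × 0.98 = 94.4% |
| 5% | 0.982 × 0.95 = 93.3% | 0.963 × 0.95 = 91.5% |
| 10% | 0.982 × 0.90 = 88.4% | 0.963 × 0.90 = 86.7% |

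The arithmetic floor, if every patient with an unreachable vein would otherwise succeed, is s − u. From 98.2% that is 96.2%, 93.2% and 88.2%, almost the same. The fall is smaller if some of these patients already fail for another reason.

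**Step 3: pooled rate.** With a share w of patients on V1.4, and V1.3 read as accessible veins, the pooled rate is s × (1 − w × u). The documents do not give w. With w = 50% and u = 5% (both assumed), 0.982 × (1 − 0.025) = 95.7%.

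**Step 4: a field error in the same list.** The V1.4 list tests RF applications on F21000010, which that list also uses for the catheter. The V1.3 list and Table 9 use F20001000.

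**The case against.** The strongest reply is that the version-specific lists define only the PVAC-GOLD-only condition, while Table 9 implements the accessible-vein condition separately, with the same six fields on both forms. That is correct, and it rules out the broader inference that the SAP fails to implement the criterion at all. It does not rescue patient B: meeting the third condition does not help a patient who has failed the second.

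A second reply is that everything turns on a form the text does not show. The label printed for F22000062 may be shortened, and the form may ask about accessible veins. Protocol 7.4 says optional fields carry a not-available box or similar, so absent veins may already be coded. This stands as a limit: if the form already asks about accessible veins, the remedy shrinks to correcting the SAP wording. As written, however, the SAP would be programmed the stricter way.

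Third, hard-to-reach veins may lead to use of an irrigated catheter, as protocol 4.4.3 notes. Where that catheter achieves isolation, the patient already fails the PVAC-only condition. This also stands, and it is why the figures above are treated as about the lowest values.

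Finally, the endpoint is ancillary and descriptive, and the SAP openly calls the V1.3 classification assumed. That limits the consequence but does not make the two rules agree.

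**Conclusion.** The point holds in a limited form. As printed, the V1.4 rule can fail a patient who meets the stated criterion, and the same patient can pass on V1.3. For a true rate of 98.2%, the V1.4 rate would be at lowest about 96.2%, 93.3% or 88.4% if 2%, 5% or 10% of patients had an unreachable vein. These shares are assumptions; with none, there is no effect from this source.

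A reader might infer more, and the documents do not support it:

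- **V1.3 needs all six ticks (almost no successes), or any one tick (almost no failures).** The first would require a common left vein to be ticked alongside separate left superior and inferior veins. The second contradicts the accessible-vein condition in the same section.
- **The rule decides the EFAS or the main objective.** SAP 4.4 and 8.1.1 refer to success by PVI confirmation without pointing to these lists. The link is possible but not shown.
- **An accessory vein cannot be confirmed.** SAP Table 3 has a range for "Other accesery vein", and no confirmation field for it appears in 8.3.1, but whether one exists cannot be settled without the form.

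**What to change.** Amend SAP 8.3.1 and the derivation code as follows.

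1. On both forms, decide the isolation criterion from the per-vein block fields in Table 9: entrance and/or exit block in every accessible vein. Treat absent veins and documented unreachable veins as not applicable. Count accessible veins left untreated or not isolated as failures.
2. Decide the PVAC-only condition from catheter use, and on V1.4 also from F22000066, without letting an unreachable vein alone cause failure.
3. Report the V1.4 all-veins item, F22000062, as a second and stricter rate.
4. Show acute success by form version as a sensitivity analysis.
5. In the V1.4 list, change the RF-application field from F21000010 to F20001000.

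A simpler rule, scoring only veins with at least one application, should be avoided. It replaces accessible with treated, so a procedure stopped after some of the accessible veins would pass. The protocol synopsis and Appendix 1 both foresee procedures that end early.

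The cost is SAP wording and extra derivation work. For V1.3 patients the rate stays partly assumption-based, because V1.3 has no counterpart to F22000066 and may not record why a vein field is empty.

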### 8.3.1.1 Methodology for analysing the acute procedural success rate

Acute procedural success rate will be reported as frequency and percentages. Acute procedural success rate by patients will be calculated as number of patients with acute procedural success divided by number of patients with an attempted Phased RFA procedure. Acute procedural success rate by vein will be calculated as number of veins with electrical isolation verified divided by number of veins attempted with Phased RFA. 95% confidence intervals will be calculated using Fisher's exact method.

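### SAP 8.3.1 limits the eCRF V1.4 per-vein success percentages to patients with incomplete isolation, contradicting the unrestricted per-vein formula in SAP 8.3.1.1 and the protocol

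*SAP*

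**What the plan says.** SAP 8.3.1 gives separate rules for the two eCRF versions.

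- **V1.3:** "Percentages for success will be shown per vein for patients treated with PVAC GOLD solely", provided that at least one RF application was delivered.
- **V1.4:** the percentages are shown per vein for patients treated with PVAC GOLD and "all PVs were isolated at the end of the procedure = no and all PVs isolated by using PVAC only = no". The word *solely* is absent and the RF-application precondition is not repeated.

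A few lines earlier, the same section defines isolation by PVAC GOLD only on V1.4 by the opposite answers: "Where all PVs isolated at the end of the procedure = yes" and "Where all PVs isolated by using PVAC only = yes".

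SAP 8.3.1.1 defines the per-vein rate once, for everyone, as "number of veins with electrical isolation verified divided by number of veins attempted with Phased RFA". The protocol, under the acute procedural success objective in section 4.4.3, has the same definition: "Acute procedural success rate by vein will be calculated as number of veins with electrical isolation verified divided by number of veins attempted". Neither depends on eCRF version or outcome. For both versions, SAP 8.3.1 adds: "Unsuccessfulness per vein is considered, if the vein is not isolated or not verified".

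**The concern.** The V1.4 sentence selects patients on the result that the percentage is meant to measure. A patient in whom every vein was isolated contributes no veins to either numerator or denominator. The resulting figure describes how incomplete the incomplete procedures were, not how often an attempted vein was isolated.

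Acute procedural success is a named ancillary objective. SAP 8.4 schedules it for the interim analysis, whose results may be published. A per-vein table built from the V1.4 sentence would greatly understate vein-level success for those patients. Combining it with V1.3 would mix two different quantities.

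**Working it through.** The plan states no expected per-vein rate, so there is no figure to reproduce. The check sets the passages side by side and then sizes the difference.

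**Step 1. Population for the per-vein percentage**

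| Place | Population | Conditioned on outcome? |
|---|---|---|
| SAP 8.3.1, V1.3 | PVAC GOLD solely, RF applications > 0 | No |
| SAP 8.3.1, V1.4 | PVAC GOLD, *no* to both isolation questions | Yes |
| SAP 8.3.1.1 | Veins attempted with Phased RFA | No |
| Protocol 4.4.3 | Veins attempted with Phased RFA | No |

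The V1.4 sentence is the only one that conditions on outcome.

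**Step 2. Inputs**

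- s, share of patients with all veins isolated: 98.2% (paroxysmal) and 96.3% (persistent), the prior acute success rates in Protocol 4.4.3. Reading them as patient-level complete isolation is an assumption.
- k, veins attempted per patient: not given. Assumed 4, range 3 to 5.
- m, missed veins per incomplete patient: not given. Assumed 1, range 1 to 2. Missed veins are taken to be among those attempted.
- N = 1000, the planned enrolment, used only to show counts. The number on V1.4 is not given.

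**Step 3. Formulas**

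- V1.4 sentence as written: (k - m)/k. Since m is at least 1, the ceiling is (k - 1)/k.
- 8.3.1.1 denominator: 1 - (1 - s) × m/k.

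**Step 4. Results**

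The ceiling is 66.7%, 75% or 80% for k = 3, 4 or 5, whatever the value of s.

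For k = 4 and m = 1:

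- s = 98.2%: 18 incomplete patients. As written, 54/72 = 75.0% (exact 95% CI 63.4 to 84.5). On 8.3.1.1, 1 - 0.018 × 1/4, or 3982/4000 = 99.55% (99.3 to 99.7).
- s = 96.3%: 37 incomplete patients. As written, 111/148 = 75.0% (67.2 to 81.7). On 8.3.1.1, 1 - 0.037 × 1/4, or 3963/4000 = 99.08% (98.7 to 99.3).

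With m = 2 and k = 4, the rate as written is 50%, against 99.10% and 98.15%. Over the whole grid, the rate as written runs from 33.3% to 80% and the 8.3.1.1 rate from 97.5% to 99.6%. The intervals treat veins as independent and ignore clustering within patients.

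**Step 5. Pooling the two versions**

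Take 1000 patients, 40% of them on V1.4, 97% with complete isolation, k = 4 and m = 1 (all assumed).

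- V1.3: 600 × 4 = 2400 veins, 18 missed.
- V1.4 as written: 12 patients, 48 veins, 12 missed.
- Pooled missed share: 30/2448 = 1.2%. With all veins counted: 30/4000 = 0.75%.

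The overstatement of the missed share is 1/(1 - 0.97w), where w is the V1.4 share: 1.2-fold at w = 20%, 1.6-fold at 40% and 2.4-fold at 60%. At w = 40%, the pooled success rate moves by less than half a percentage point.

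**The case against.** The strongest reply is that SAP 8.3.1.1 carries the methodology heading and states the rate without restriction, in agreement with the protocol. On that view the V1.4 sentence only describes a display. It could also reflect the form: V1.4 added two summary questions (F22000062 and F22000066), and vein-level detail may be entered only after a *no*. Protocol 7.4 confirms that some eCRF fields open only after a leading question.

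Part of this stands. A reader might infer that the V1.4 per-vein rate is settled as a failures-only calculation. The documents do not support that, because the unrestricted formula is also in the SAP and a programmer has both texts. The accurate description is an internal contradiction.

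The rest does not remove the problem. Nothing says that 8.3.1.1 overrides 8.3.1, and the V1.4 sentence is the more specific instruction. Where this SAP deliberately sets aside a protocol rule, as in 7.2.3 and 8.1.1, it says so; here it does not. Protocol 7.4 does not name the per-vein fields as conditional, and Table 9 lists F22000010 to F22000060 for both versions. The annotated eCRF (Appendix E) is not in the text available, so entry conditions cannot be checked. If they exist, the SAP still has to say how veins of patients answering *yes* are counted.

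It is also fair to say that this is a descriptive, ancillary endpoint. The patient-level success rate has its own V1.4 definition and denominator, which this sentence does not alter.

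**Conclusion.** The point holds as a contradiction within the SAP, and between the SAP and the protocol, over the V1.4 per-vein population. If the V1.4 sentence is followed, the rate is capped at 75% with four veins, against about 99% on the 8.3.1.1 denominator, and cannot be pooled with V1.3. These sizes rest on assumed vein counts and on reading the protocol's prior success rates at patient level. The direction does not, provided that the non-isolated vein was one of those attempted.

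Three stronger readings are not supported.

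- **That the V1.4 table would be meaningless.** A breakdown of which veins were missed in incomplete procedures is legitimate description. It just is not the per-vein success rate.
- **That the restricted set is the set of endpoint failures.** Patients whose veins were all isolated, but not by PVAC alone, also fail the composite definition. The double *no* leaves them out.
- **That the main objective is affected.** SAP 8.1 does not use the per-vein rate.

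The text should be corrected before the final analysis.

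**What to change.** In SAP 8.3.1:

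1. Delete the restriction to *no* on both questions. Use one denominator for both eCRF versions: veins attempted with Phased RFA in all attempted procedures, as in 8.3.1.1.
2. Report the rate separately for PVAC GOLD solely and not solely, as 8.3.1 already plans for success rates. For the former, restore *solely* and RF applications > 0 in the V1.4 text. The 8.3.1.1 denominator itself has no PVAC GOLD restriction and should not be described as having one.
3. Take vein status from the per-vein block fields F22000010 to F22000060 for both versions.
4. Check the annotated eCRF. If V1.4 opens those fields only after a *no*, state that a *yes* to F22000062 counts as verified isolation of all attempted veins. Reconcile this with the rule that a vein not verified is unsuccessful (8.3.1) and with the rule that missing values are not replaced (7.5.1).
5. Label any table limited to *no* answers as a supplementary description of incomplete isolations.

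The cost is a few sentences and one check of the annotated eCRF. No new data are needed. Step 4 is the only part that takes thought, since it may require an explicit derivation rule.
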